Pharmacokinetics of *Centella asiatica* in the Elderly

NCT03929250

STUDY PROTOCOL INCLUDING STATISTICAL ANALYSIS PLAN

Document Version Date: February 28, 2024

Study Title: A pharmacokinetic study of *Centella asiatica* in the elderly

Principal Investigator: [name]

IRB#: 17697

Date: Feb 28 2024

Protocol v4.0

Title: A pharmacokinetic study of *Centella asiatica* in the elderly

A. OBJECTIVES

A.1. Purpose

The purpose of this pilot study is to measure the oral bioavailability and pharmacokinetics of known bioactive compounds from a standardized *Centella asiatica* water extract product (CAP) in cognitively healthy elders. Compound levels will be measured in human plasma and urine over 12 hours after acute oral administration of two doses of the botanical extract product. The dose giving maximum plasma levels (C_{max}) closest to those observed in our mouse studies, as well as the rate of clearance ($t_{1/2}$) of the known compounds, will be identified. These data will be used to inform decisions on the dosage and dosing frequency for future phase 1 and phase 2 clinical trials.

A.2. Primary goal

To determine the oral bioavailability and pharmacokinetics of known compounds from two single administrations of a *Centella asiatica* product in non-demented elders.

A.3. Endpoints

- The primary endpoints for this study are the maximum concentration (C_{max}), the area under the curve (AUC), and the time of maximum concentration (t_{max}) of known compounds from *Centella asiatica* (triterpenes and caffeoylquinic acids and their metabolites) in human plasma.
- A secondary endpoint is the half-life ($t_{1/2}$) of the known bioactive compounds and their metabolites to help determine dosage intervals.
- Additional secondary endpoints include temporal changes in ferric reducing ability of plasma (FRAP) as an indicator of antioxidant potential over time, tolerability and detection of acute adverse events through monitoring by participant interviews, biometrics, vital signs and questionnaires.

B. SPECIFIC AIMS

Aim 1: To assess the bioavailability and rate of clearance of *Centella asiatica* derived compounds in cognitively healthy elders through a pharmacokinetic study.

- **Hypothesis:** We hypothesize that the triterpene and caffeoylquinic acid components from *Centella asiatica* will be bioavailable, and a dose giving similar plasma levels to those associated with cognitive effects in mice can be achieved.

Aim 2: To determine the acute tolerability of a *Centella asiatica* product in cognitively healthy elders.

- **Hypothesis:** We hypothesize that acute usage of the *Centella asiatica* product will be well tolerated and produce no severe adverse events.

C.BACKGROUND

C.1. Alzheimer's disease

Alzheimer's disease is a severe form of cognitive impairment and one of the most expensive and debilitating conditions known to modern medicine. The National Institute of Aging suggests that greater than five million Americans may have Alzheimer's disease, making it the sixth leading cause of death in the United States.¹ In 2016 alone, government health agencies

Study Title: A pharmacokinetic study of *Centella asiatica* in the elderly

Principal Investigator: [name]

IRB#: 17697

Date: Feb 28 2024

Protocol v4.0

(Medicare and Medicaid) spent an estimated \$160 billion on Alzheimer's disease with a projected 365% increase by 2050.²

The pathogenesis of Alzheimer's disease is highly complex. Current evidence suggests it is a combination of genetics, environment and lifestyle factors making the development of treatments very challenging. Its most striking pathological feature is the accumulation of β -amyloid (A β) plaques within the brain.³ Current pharmaceutical investigation is aimed at preventing the accumulation of, or promoting the clearance of these neurotoxic plaques (anti-amyloid immunotherapy)^{4,5}; however, recent trials of such agents have failed to produce a significant clinical effect on Alzheimer's disease.^{6,7} Drugs currently FDA-approved for the symptomatic treatment of Alzheimer's disease are either cholinesterase inhibitors⁸ or act at the N-methyl-D-aspartate (NMDA) receptor.^{9,10} Unfortunately, these treatments do not influence disease progression, and their effectiveness is highly variable.

Beyond cognitive impairment, Alzheimer's disease also has significant comorbidities including insomnia, depression¹¹ and anxiety.¹² Multiple interventions are often needed to manage these symptoms affecting patient compliance and safety. This warrants further investigation into effective, inexpensive and well-tolerated treatments for Alzheimer's disease and its comorbidities.

Gender differences have been observed in the incidence, development and progression of Alzheimer's disease, and in response to interventions targeting cognitive impairment. Women develop cognitive disability more rapidly compared to men.^{13,14} Previous studies of intranasal insulin for cognition showed functional abilities were better preserved in women compared to men.¹⁵ These differences highlight the importance of evaluating responses to any agent in both males and females. As part of this proposed project we will evaluate potential gender differences in bioavailability and pharmacokinetics.

C.2. *Centella asiatica*

Centella asiatica is a highly regarded botanical reputed in Eastern medicine to increase intelligence and memory.¹⁶ In Western countries, it is sold as the dietary supplement "gotu kola"¹⁷ for use in improving brain health and cognitive function. Preclinical studies have shown that *Centella asiatica* extracts have biological effects of relevance to memory, learning, aging, mood and potentially disease progression in Alzheimer's disease.¹⁸ Water extracts of *Centella asiatica* have improved learning and memory in wild-type rats,¹⁹ wild-type mice,^{20,21} and rats subjected to central nervous system toxicity.^{22,23} In addition, similar extracts have been shown to modify the brain structure by increasing hippocampal neuron dendritic arborization in adult rats,²⁴ neonatal rats,²⁵ and neonatal mice,²¹ potentially contributing to the observed cognitive changes. With regards to mood and behavior, ethanol extracts given to mice subjected to chronic and acute stress²⁶ and sleep deprivation²⁷ demonstrated anxiolytic properties. Similar ethanol extracts revealed antidepressant properties in rats.²⁸

Figure 1. *Centella asiatica* water extract improves learning and memory in aged female Tg2576 mice without altering β -amyloid accumulation. Tg2576 mice (20 month old) were exposed to *Centella asiatica* water extract (200mg/kg/day) in their drinking water for 2 weeks before and during testing (total 5 weeks). Left – Morris water maze escape times. Right – Soluble and insoluble fractions of A β were extracted from cortical tissue and analyzed via ELISA (bars represent means +/- standard error).

[figure not shown]
Study Title: A pharmacokinetic study of *Centella asiatica* in the elderly

Principal Investigator: [name]

IRB#: 17697

Date: Feb 28 2024

Protocol v4.0

With applications specific to Alzheimer's disease, one study showed that long-term usage of a *Centella asiatica* extract (six months) reduced β -amyloid plaque burden in a mouse model of Alzheimer's disease²⁹; however, studies performed at Oregon Health and Science University (OHSU) suggest that water extracts of *Centella asiatica* may achieve its cognitive effects without a direct action on β -amyloid (Figure 1).³⁰ Rather, *Centella asiatica* appears to affect downstream targets protecting neurons from β -amyloid induced neurotoxicity.^{20,31,32} This suggests that *Centella asiatica* may be able to limit disease progression even when β -amyloid deposition has already taken place, thereby representing a novel treatment mechanism, potentially complementary to the medications in development.

Human studies, although limited, support *Centella asiatica*'s ability to affect cognition and mood. Placebo-controlled trials showed that herbal extracts, or dried herb, improved cognitive function in healthy elderly³³ and middle-aged³⁴ volunteers. In elderly participants with mild cognitive impairment, investigators found improvements in cognitive test results (Mini Mental State Examination) following use of dried *Centella asiatica* for six months³⁵; however, no control group was incorporated. Unfortunately, these studies used highly variable *Centella* preparations that were poorly characterized and were either performed in cognitively normal individuals thereby limiting clinical applicability, or were not placebo-controlled. This warrants a robust, randomized, double blind, placebo-controlled study in cognitively impaired humans to examine the effects of a chemically well-characterized *Centella asiatica* extract on cognition.

C.3. Phytochemistry

Botanical agents are complex mixtures that show considerable variability due to growth conditions, geography, the parts utilized and preparation method.^{36,37} Limited regulation of the production of these agents makes the efficacy of commercial products unpredictable. To this end, it is imperative that pharmacokinetic and clinical studies of botanicals use botanically authenticated, chemically well-characterized, stable products that are standardized to a specific content of active ingredients.

Chemical analyses of *Centella asiatica* performed by our group and others have identified unique substances known as triterpenoid saponins (asiatic acid, madecassic acid, asiaticoside

Study Title: A pharmacokinetic study of *Centella asiatica* in the elderly

Principal Investigator: [name]

IRB#: 17697

Date: Feb 28 2024

Protocol v4.0

and madecassoside),^{38,39} which are believed to be associated with *Centella asiatica*'s neuroprotective and neurotropic effects.⁴⁰⁻⁴³ Previous pharmacokinetic studies of *Centella* products have focused primarily on these compounds (most specifically asiatic acid) in plasma using purified extracts or synthesized compounds.⁴⁴⁻⁴⁶ Our group has found, using high performance liquid chromatography coupled to mass spectral detection (HPLC-MS), additional active phenolic components known as caffeoylquinic acids in water extracts of *Centella*.³¹ These acids have been shown to protect against excitotoxic and hypoxic damage⁴⁷ and β-amyloid toxicity in primary neurons.^{31,48} To date, there are no pharmacokinetic studies of caffeoylquinic acids and triterpenes from water extracts of *Centella asiatica* in humans. This project aims to investigate the bioavailability of all of the aforementioned compounds from a water extract of *Centella asiatica* in human plasma and urine.

C.4. Safety

Centella asiatica is an edible plant and the Botanical Safety Handbook⁴⁹ classifies it as a Class 1 herb that can safely be consumed when used appropriately. The widespread use of *Centella* as a dietary supplement and the available human studies support its safety.^{17,33-35} The recommended dose of this herb, which is consumed in India and Sri Lanka as a healthy addition to the diet, is between 0.5 and 1.5 g dried leaf daily.^{16,17} In multiple human studies using the fresh or dried whole herb, or in many clinical studies using extracts of *Centella asiatica*, no adverse effects were reported.^{35,50-53} There have also been several clinical studies in which multi-component products containing *Centella asiatica* herb or extracts were found to be well tolerated.⁵⁴⁻⁶⁰ One study in which elderly participants consumed dried herb (1000 mg per day for 6 months) found no change in their liver enzymes (Serum glutamic oxaloacetic transaminase (SGOT) or serum glutamic-pyruvic transaminase (SPGT)).³⁵ In another study, administration of a concentrated extract at 750mg or 1000 mg per day daily for six weeks caused no change in liver enzymes Alanine Aminotransferase (ALT) and Aspartate Aminotransferase (AST) levels.⁶¹ Two clinical studies on polyherbal preparations containing *Centella asiatica* (albeit in small quantities) also reported no changes in safety laboratory results.^{54,57}

TTFCA (a purified triterpene mixture), was well-tolerated at all of the following doses in microcirculation studies: 30 or 60mg daily for 7 days⁶²; 30 or 60 mg administered twice daily for 6 months⁶³; and 60mg twice daily for 12 months.⁶⁴ Two studies on femoral and carotid plaque formation respectively^{65,66} both used TTFCA at 180mg daily for 12 months. Again, TTFCA was well tolerated at this highest reported dose.

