Centella asiatica shows remarkable cognitive enhancing and neuroprotective properties in extensive preclinical research performed by our group and by others (Section C.2.). The small number of human clinical studies favors the use of *Centella asiatica* as a dietary supplement to improve cognitive function and brain health; however, limited regulation of these agents makes efficacy of commercial products unpredictable. Our ultimate goal is to develop an FDA-

Study Title: A pharmacokinetic study of *Centella asiatica* in the elderly

Principal Investigator: [name]

IRB#: 17697

Date: Feb 28 2024

Protocol v4.0

approved, standardized, botanical extract of *Centella asiatica* for evidence-based treatment of mild cognitive impairment and Alzheimer's disease.

This is the first human pharmacokinetic study of a standardized crude water extract of *Centella asiatica*. Previous pharmacokinetic studies have used refined combinations of *Centella*'s unique triterpenes.⁴⁴⁻⁴⁶ Use of such extracts eliminates possible chemical interactions and bioactive synergistic compounds that may result from crude extract preparation. Mouse studies have shown improvements in cognition in wild-type and Alzheimer's disease models using crude water extracts with or without triterpenes^{20,30} suggestive of other neuroactive ingredients within *Centella asiatica* water extract. These appear to include caffeoylquinic acids and potentially other unidentified compounds. This study will preserve possible synergistic effects by using a crude water extract, but also standardize the product to the known bioactive constituents, which has not been done in previous human trials. In addition to studying the triterpenes, this study will investigate the pharmacokinetics and bioavailability of *Centella* derived caffeoylquinic acids and their metabolites, which has not been previously evaluated. The observed pharmacokinetic profile will inform dosage decisions and dosing frequency for future human clinical trials.

E. PRELIMINARY DATA

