Power analysis and sample size estimation for the dose-dependent pharmacokinetics of *Centella asiatica* analytes were derived from the literature, specifically the plasma dose response analysis of the triterpene asiatic acid by Grimaldi et. al.⁴⁵ after single acute administration of 30 mg and 60 mg of a *Centella asiatica* triterpene fraction. In a repeated measures cohort of 12 males, they found significant differences ($p<0.05$) in asiatic acid's peak plasma concentration (C_{max}) (30 mg: $0.70 \mu\text{g/ml} \pm 0.38$; 60 mg: $1.36 \mu\text{g/ml} \pm 0.45$; $d=1.57$) and 24-hour total bioavailability (AUC_{0-24}) (30 mg: 4.16 ± 3.81 ; 60 mg: 9.39 ± 3.53 ; $d=1.42$) between the two doses. This paper was chosen as an analog for the current study since a proportionally equimolar dose response shift in the pharmacokinetic profile of asiatic acid can be expected of the proposed *Centella asiatica* product doses. Under that assumption, a significant within-group dose response at $\alpha=0.05$ with at least 80% power would be found for C_{max} with six participants and for AUC_{0-12} with seven participants. Even if the inclusion of additional compounds in the

Study Title: A pharmacokinetic study of *Centella asiatica* in the elderly

Principal Investigator: [name]

IRB#: 17697

Date: Feb 28 2024

Protocol v4.0

water extract reduces the dose effect anticipated in the current study, a significant difference in the pharmacokinetic outcomes would still be seen with eight participants. We therefore, propose a cohort of four men and four women, which will enable dose responses to be seen within each gender individually, and allow for evaluation of an attenuated response by pooling gender or provide protection against study dropout.

L.3. Data quality and management

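### The general power claims in L.2 and F.2.1 rest only on asiatic acid Cmax and AUC: they are unsupported for the caffeoylquinic acids and cannot extend to tmax, although both are primary

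*Combined protocol and SAP*

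**What the plan says.** A.3 lists three primary parameters, Cmax, AUC and "the time of maximum concentration (t_{max}) of known compounds from *Centella asiatica* (triterpenes and caffeoylquinic acids and their metabolites) in human plasma". L.1 then tests dose effects for all continuous variables, with paired t-tests first and a two-sided 5% level.

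L.2 opens broadly: "Power analysis and sample size estimation for the dose-dependent pharmacokinetics of *Centella asiatica* analytes were derived from the literature". The source is narrower, "specifically the plasma dose response analysis of the triterpene asiatic acid", taken from one study of 12 males given 30 mg and 60 mg of a triterpene fraction. The only inputs are Cmax and AUC0-24 of that compound. L.2 assumes that the asiatic acid profile will shift in proportion to dose, and concludes that a dose response "with at least 80% power would be found for C_{max} with six participants and for AUC_{0-12} with seven participants".

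Two further statements carry no such limit. L.2 says that even if other compounds in the extract weaken the dose effect, "a significant difference in the pharmacokinetic outcomes would still be seen with eight participants". F.2.1 says that power for differences between doses is kept if a quarter of the participants drop out and six remain.

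On the caffeoylquinic acids, section D says the study will examine the kinetics of the plant's "derived caffeoylquinic acids and their metabolites, which has not been previously evaluated". C.3 adds that no human study has yet looked at these compounds or the triterpenes from water extracts of the plant.

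**The concern.** The power property is stated for more than its basis covers. Two parts of the primary set lie outside that basis: every caffeoylquinic acid and metabolite, and tmax for all analytes.

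The caffeoylquinic acids are, by section D, the trial's new contribution. If the dose comparison for one of them gives p>0.05, a reader who relies on the general claim may take it as evidence of no dose response from an adequately powered comparison. Nothing in L.2 would justify that, because no expected effect or variability for these compounds entered the calculation. The results are meant to inform dose and frequency in later trials (A.1), so the distinction between no difference and no information matters.

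**Working it through.** **Inputs.** From L.2: Cmax 0.70 (SD 0.38) and 1.36 (SD 0.45), d = 1.57; AUC0-24 4.16 (SD 3.81) and 9.39 (SD 3.53), d = 1.42; 80% power. From L.1: paired t-test, two-sided 0.05.

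**1. Reproduce the plan's figures.** SD of the paired difference = √(s1² + s2² − 2·r·s1·s2). L.2 does not state r. With r = 0.5:

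- Cmax: √(0.1444 + 0.2025 − 0.1710) = 0.419; 0.66/0.419 = 1.574.
- AUC: √(14.516 + 12.461 − 13.449) = 3.678; 5.23/3.678 = 1.422.

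Both match the stated d. Power comes from the noncentral t distribution with n − 1 degrees of freedom and noncentrality d√n.

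| Asiatic acid | n=5 | n=6 | n=7 | n=8 |
|---|---|---|---|---|
| Cmax, d=1.57 | 74.7% | 86.3% | 93.0% | 96.6% |
| AUC, d=1.42 | 66.6% | 79.2% | 87.6% | 92.9% |

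The smallest n reaching 80% is six and seven, as L.2 says. The result depends on r: with r = 0 the numbers become nine and ten; with r = 0.3, seven and eight.

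**2. How much weakening eight participants allow for asiatic acid.** 80% power at n=8 needs a standardized paired difference of 1.156. Since 1.156/1.57 = 0.74 and 1.156/1.42 = 0.81, d may fall by about 26% (Cmax) or 19% (AUC). L.2 gives no figure for the weakening it has in mind.

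**3. tmax.** If the 4 g curve is a constant multiple of the 2 g curve, its peak lies at the same time. The expected paired difference is 0, the noncentrality is 0, and nominal power equals the 5% error rate at n=6, at n=8 and at any other n. As an illustration, a linear one-compartment curve (assumed absorption rate 1.2/h, elimination rate 0.2/h) on the plan's sampling times gives, when the dose doubles, Cmax 1.39 to 2.78, AUC 8.93 to 17.86, and tmax 2.0 h both times.

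**4. Caffeoylquinic acids.** L.2 contains no input for them. The mouse profile described with Figure 2 used one dose, 200 mg/kg, and four animals were euthanized per time point. Whatever the figure shows, that design gives no dose contrast and no within-animal variability. Power can therefore be shown only over an assumed range:

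| Assumed standardized paired difference | Power, n=8 | Power, n=6 |
|---|---|---|
| 0.50 | 23% | 17% |
| 0.75 | 45% | 32% |
| 1.00 | 68% | 51% |
| 1.25 | 86% | 69% |

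80% power needs about 1.16 at n=8 and 1.43 at n=6. Nothing available places any caffeoylquinic acid on this scale.

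**The case against.** The best defence is that L.2's one numeric sentence names its parameters, Cmax and AUC0-12, and that the outcomes in the sentence on eight participants may mean just those two. L.2 also calls the cited paper an analog and marks the result as conditional on its assumption. This is a pilot whose goal in A.2 is estimation, a primary pharmacokinetic parameter need not carry a powered dose comparison, and L.1 already plans descriptive summaries by dose. All of this is fair, and it means that L.2 makes no explicit power claim for tmax. It does not remove the mismatch: L.2's opening speaks of analytes in general, F.2.1 names neither analyte nor parameter, and L.1 applies the dose test to all continuous variables.

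Three stronger readings are tempting and should be resisted.

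- A reader might infer that the trial is underpowered for the caffeoylquinic acids. The documents do not show this. Nor can one say that they hold no variability figure for these compounds: the body of Table 1 and the panels of Figure 2 are not readable in the text available.
- A reader might turn the requirement of 1.156 into a ceiling on within-person CV, about 44% for a doubled exposure on the log scale (ln 2/(√2 × 1.156) = 0.424; √(exp(0.424²) − 1) = 0.44). That fails as a general rule. Converting L.2's AUC figures to the log scale (assuming lognormal data and r = 0.5) gives asiatic acid a CV of about 51% but power of about 96% at n=8, because the implied geometric ratio is about 2.9, not 2.
- A reader might infer that the plan intends to read p>0.05 as no dose response. No section says so. A.1 ties dose choice to the closeness of human Cmax to mouse levels. The misreading is a risk that the wording leaves open.

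**Conclusion.** The point holds as one of scope. The calculation in L.2 is correct for asiatic acid Cmax and AUC under a within-person correlation of 0.5. The general statements for eight (L.2) and six (F.2.1) go beyond it. For caffeoylquinic acids and their metabolites the claim lacks support; actual power could be high or low. For tmax the claim cannot apply under L.2's own assumption. That conclusion rests on reading the assumption as a scaling of the whole curve; saturable absorption could move tmax, but the plan neither assumes nor quantifies it. The 5% is nominal, since tmax falls on a coarse set of sampling times and ties are likely. Nothing here argues for a larger trial.

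**What to change.** - **L.2 and F.2.1:** limit the power statements to Cmax and AUC of asiatic acid, state the assumed within-person correlation (0.5 reproduces the given d), and note that the AUC input is AUC0-24. For six participants, give 86% for Cmax and 79% for AUC. Say that no power is claimed for caffeoylquinic acids, their metabolites or tmax.
- **L.1:** report the within-person 4 g/2 g ratio of Cmax and AUC0-12 with a 95% interval for every analyte, and state that p>0.05 will not be read as absence of a dose response.
- **A.3 and L.1:** keep tmax as a primary parameter but summarise it by median and range per dose, outside the powered dose comparison.

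The cost is a narrower power claim and a little more analysis. No participants, visits or samples are added.
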